4.4 Method of Assigning Subject Identification

After informed consent has been obtained, the subject must be enrolled into the study by using an interactive response technology (IRT) to obtain the subject number. The exact procedure for using the IRT will be detailed in a separate document.

In BMS-986183 dose escalation (Part 1) and BMS-986183 and nivolumab dose escalation (Part 3), if a subject discontinues treatment with BMS-986183 during the DLT period for reasons other than DLT, the subject may be replaced if necessary for safety assessments. Replacement subjects will receive the same treatment but will be assigned a new subject number.

Subjects may be permitted to rescreen for the study following agreement between the Sponsor/medical monitor and investigators.

4.5 Selection and Timing of Dose for Each Subject

Each subject will be assigned to a specific dose level as listed in sequential order during BMS-986183 dose escalation (Part 1) and BMS-986183 and nivolumab dose escalation (Part 3) (see Section 3.1.1). Subjects in BMS-986183 dose expansion (Part 2) and BMS-986183 and nivolumab dose expansion (Part 4) will be enrolled at or below the MTD (or MAAD for BMS-986183 and nivolumab dose expansion [Part 4]) as agreed upon by the Sponsor/medical monitor and investigators (Section 3.1.2).

4.5.1 Dose Limiting Toxicities

For the purpose of guiding dose escalation, DLTs will be defined based on incidence, intensity, and duration of AEs for which no clear alternative cause is identified. The DLT evaluation period for dose escalation in BMS-986183 dose escalation (Part 1) and BMS-986183 and nivolumab dose escalation (Part 3) is 21 days. AEs will be graded according to the NCI CTCAE v4.03. For the purpose of subject management, any AE that meets DLT criteria, regardless of the cycle in which it occurs, will lead to dose interruption. Subjects who withdraw from the study during the DLT evaluation interval for reasons other than a DLT may be replaced at the same dose level. The incidence of DLT(s) during the first cycle of treatment (the DLT evaluation period) will be used in dose-escalation decisions and to define the MTD. AEs occurring after the DLT period will be

considered for the purposes of defining the MTD, upon agreement between the Sponsor/medical monitor and investigators, if they are determined to have no clear alternative cause and are not related to disease progression.

DLT(s) will be defined as any of the following events unless a clear alternative cause is identified:

Hepatic DLT

Hepatic DLT for which no clear alternative cause is identified (e.g. disease progression, hepatitis flare, other concomitant medications) and meets the following criteria

- AST or ALT > $10 \times ULN$ for > 2 weeks
- AST or ALT > $15 \times$ ULN irrespective of duration
- Total bilirubin > 8 × ULN irrespective of duration for subjects with elevated total bilirubin at study entry or > 5 × ULN for those with normal total bilirubin at entry
- Concurrent ALT ≥ 10 × ULN AND total bilirubin ≥ 2 × ULN or baseline value (if elevated bilirubin at study entry), AND no other immediately apparent possible causes of ALT elevation and hyperbilirubinemia. (For definition of potential drug-induced liver injury [p-DILI], see Section 6.6.)
- Clinical deterioration manifested by drug-related hepatic decompensation not identified above

Nonhematologic DLT

Any of the following events will be considered a nonhematologic DLT:

- ≥ Grade 3 infusion-related reactions that recur despite appropriate medical management as in Section 3.7.
- (BMS-986183 and nivolumab dose escalation [Part 3] only) ≥ Grade 2 episcleritis, uveitis, or iritis.
- (BMS-986183 and nivolumab dose escalation [Part 3] only) Grade 2 or greater eye pain or reduction of visual acuity that does not respond to topical therapy and does not improve to Grade 1 severity within 2 weeks of starting therapy or requires systemic treatment.
- \geq Grade 3 nonhematologic toxicity, with the following exceptions.

The following Grade 3 or greater nonhematologic events will NOT be considered DLTs:

- ≥ Grade 3 electrolyte abnormalities that are not complicated by associated clinical AEs, are not clinically significant, last less than 72 hours and either resolve spontaneously or respond to conventional medical intervention
- Grade 3 nausea, vomiting or diarrhea that lasts less than 48 hours and either resolves spontaneously or responds to conventional medical intervention
- Isolated Grade 3 fever not associated with hemodynamic compromise (ie, hypotension, clinical or laboratory evidence of impaired end-organ perfusion)
- Grade 3 or 4 elevation of amylase or lipase not associated with clinical or radiographic evidence of pancreatitis

- Grade 3 endocrinopathy that is well controlled by hormone replacement
- Grade 3 fatigue for \leq 7 days
- Grade 3 infusion reaction that returns to Grade 1 in less than 6 hours

Hematologic DLT

- Grade 4 neutropenia \geq 7 days in duration
- Grade 4 febrile neutropenia of any duration
- Grade 3 febrile neutropenia that lasts > 48 hours
- Grade 4 thrombocytopenia or Grade \geq 3 thrombocytopenia associated with clinically significant bleeding
- Grade 4 anemia

4.5.2 Guidelines for Dose Modifications

Subjects will be monitored continuously for AEs while on study therapy. Subjects will be instructed to notify their physician immediately for any and all AEs. For the purposes of subject management, drug-related AEs occurring at any time that meet the DLT definition will lead to dose interruption, dose modifications, and/or permanent discontinuation of study drug as defined in Table 4.5.2-1 and in this section. The criteria presented in this section and Table 4.5.2-1 for dose modifications and delays are meant as general guidelines:

- Subjects will continue to receive therapy as long as they have not had disease progression or drug-related AE requiring dose modification as described below.
- Dose modification, interruption, or delay may occur in the setting of lower grade AE and/or be more conservative than indicated in Table 4.5.2-1 based on the clinical judgment of the investigator, and in consultation with the Sponsor/medical monitor.
- Dose reductions should be to the previous lower dose level.
- If several AEs of varying grade or severity occur simultaneously, the dose modification applied should be the greatest reduction applicable.
- Assessment of causality (chronology, confounding factors such as disease, concomitant medications, diagnostic tests and previous experience with the agent) must be determined and documented by the investigator, prior to dose modification.
- If the same > Grade 3 nonhematologic AE recurs despite a dose reduction, a second dose reduction vs discontinuation of the subject from further protocol therapy will be discussed and agreed upon by the Sponsor/medical monitor and investigators.
- Subjects who experience a Grade 4 nonhematologic AE, except for Grade 4 electrolyte abnormalities (see Table 4.5.2-1), will not receive additional protocol-related therapy and will be removed from study unless discussed and agreed upon by the Sponsor/medical monitor and investigators that it is in the best interest of the subject to receive additional therapy with BMS-986183 (for example, if the subject has demonstrated a response to therapy).
- No more than 2 dose reductions will be allowed per subject. If a third dose reduction is required the subject must discontinue study drug. Dose re-escalation after a dose reduction may occur

in limited circumstances (such as a change in attribution of an AE) after discussion and agreement of the Sponsor/medical monitor and investigators.

- For an AE requiring dose modification, BMS-986183 should be interrupted to allow recovery from the AE. Re-initiation of study drug cannot occur until AE decreases to ≤ Grade 1 or baseline assessment. In case of delayed recovery to ≤ Grade 1 or baseline (except for alopecia or fatigue) from treatment-related AEs that results in a delay of treatment for > 6 weeks, the subject will not receive additional protocol-related therapy and will be removed from study unless discussed and agreed upon by the Sponsor/medical monitor and investigators that it is in the best interest of the subject to receive additional therapy with BMS-986183 (for example, if the subject has demonstrated a response to therapy).
- During the DLT evaluation period, if a subject is dose reduced and experiences a DLT at the lower dose, this DLT will be attributed to the highest dose level administered.
- Dose reductions for nivolumab will not be permitted for individual subjects.

For data collection and analysis purposes, all subjects will continue to be classified by the original treatment arm.

Dose Modification Criteria for Drug-Related Adverse Events	BMS-986183 (modification at next dose)
Grade 4 neutropenia lasting > 5 days	Decrease 1 level
Grade 3 febrile neutropenia lasting > 48 hours	Decrease 1 level
Grade 4 febrile neutropenia	Discontinue
Grade 4 thrombocytopenia or ≥ Grade 3 thrombocytopenia with significant bleeding	Decrease 1 level
QTcF > 500 msec confirmed by at least 1 repeat ECG and at least 60 msec above baseline	Interrupt if needed to optimize electrolyte management. If persists after electrolyte optimization (including dose modification of BMS-986183, if necessary), discontinue.
Grade 1 Troponin I or T confirmed when repeated in 72 hours	Discontinue
Grade 3 Troponin I or T	Discontinue
AST/ALT/total bilirubin elevation per Section 4.5.3	Decrease 1 level
\geq Grade 3 infusion-related reaction	See Section 3.7
\geq Grade 3 peripheral neuropathy	Discontinue
Any other drug-related \geq Grade 3 nonhematologic AE except in subjects not receiving maximum medical management or electrolyte abnormalities that may be managed with supplements	Decrease 1 level

Table 4.5.2-1:Dose Modifications

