 - v) Cardiovascular disease-related requirement for daily supplemental oxygen therapy
 - vi) QTcF prolongation > 480 msec
 - vii) Valvular heart disease > CTCAE Grade 2
 - viii) Cardiac Troponin T (cTnT) or $I \ge 2 \times$ institutional ULN. Subjects with cTnT or cTnI levels between > 1 to $2 \times$ ULN will be permitted if repeat levels within 24 hours are $\le 1 \times$ ULN.
 - ix) LVEF < 50% as measured by 2-D echocardiography.
- c) NCI CTCAE v4.03 Grade 2 or higher peripheral neuropathy (sensory or motor)
- d) Thrombotic or embolic events (except HCC tumor thrombus) within the past 6 months, such as cerebrovascular accident (including transient ischemic attacks), pulmonary embolism
- e) Any other hemorrhage/bleeding event ≥ CTCAE Grade 3 within 8 weeks except for esophageal or gastric varices (Target disease exception 1.e.)
- f) Major surgical procedure, open biopsy, or significant traumatic injury within 4 weeks prior to start of investigational product (IP) administration or those who receive minor surgical procedures (eg, core biopsy or fine needle aspiration) within 1 week prior to the start of IP.

- g) Prior malignancy active within the previous 3 years except for locally curable cancers that have been apparently cured, such as basal or squamous cell skin cancer, superficial bladder cancer, or carcinoma in situ of the prostate, cervix, or breast.
- h) Any serious or uncontrolled medical, psychiatric, and/or social reason that in the opinion of the investigator may increase the risk associated with study participation or study drug administration, impair the ability of the subject to receive protocol therapy, or interfere with the interpretation of study results.
- i) Subjects in all study parts except BMS-986183 and nivolumab dose expansion (Part 4): All toxicities attributed to prior anti-cancer therapy other than alopecia, and fatigue must have resolved to Grade 1 (NCI CTCAE v4.03) or baseline before administration of study drug.
- j) Subjects in BMS-986183 and nivolumab dose escalation (Part 3) and BMS-986183 and nivolumab dose expansion (Part 4): Prior organ allograft or allogeneic bone marrow transplantation.

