4.5.4 Dose Delays Due to Toxicity

Subjects who experience the following must have study drug held:

- Potential DLTs (DLT per definition, are related to study drug), until DLT relatedness is defined. In BMS-986183 and nivolumab dose escalation (Part 3) and BMS-986183 and nivolumab dose expansion (Part 4), every attempt must be made to assign relationship to BMS-986183, to nivolumab, or to both.
- Elevated AST or ALT as defined in Section 4.5.3.1.
- Grade 1 Troponin T or I elevation until confirmation (until repeat Troponin is $\leq 1 \times$ ULN) within 24 hours. (Subjects with repeat Troponin I or T > 1× ULN will be discontinued.)
- AE, laboratory abnormality, or concurrent illness that, in the judgment of the Investigator, warrants delaying the dose of study drug.

Nivolumab in combination with BMS-986183 administration should be delayed for the following:

- Any > Grade 2 non-skin, drug-related AE, with the exception of fatigue
- Any > Grade 3 skin, drug-related AE
- Any > Grade 3 drug-related laboratory abnormality (excluding AST/ALT or total bilirubin), with the following exceptions:
 - Grade 3 lymphopenia does not require dose delay.
 - Any \geq Grade 3 drug-related amylase or lipase abnormality that is not associated with symptoms or clinical manifestations of pancreatitis does not require dose delay.
- Any AE, laboratory abnormality, or intercurrent illness that, in the judgment of the investigator, warrants delaying the dose of study medication

Subjects who require delay of BMS-986183 and/or nivolumab should be re-evaluated weekly or more frequently if clinically indicated and resume study drug dosing when retreatment criteria are met.

Subjects eligible to resume study therapy can resume treatment(s) after at least 21 days from the last dose. Subjects who meet criteria listed in Section 4.5.6 are required to permanently discontinue study drug. All other subjects will be permitted to resume therapy with study drug following resolution of the AE as described in Section 4.5.2.

Extensions to the period of dose delays > 6 weeks may be granted for individual subjects on a case-by-case basis after specific consultation and agreement between the investigator and BMS medical monitor in settings where benefit/risk may justify continued study therapy (eg, subject deriving clinical benefit who requires prolonged steroid taper for the management of non-DLT drug related AEs, or experiences delays for the management of a non-drug-related AE).

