Sites should collect these screening samples between -28 to -1 days from enrollment to ensure that results required for eligibility purposes are verified prior to registration. Pregnancy testing (serum or urine) for WOCBP must be performed within 24 hours prior to the initial administration of IP at baseline and then prior to administration of study drug during study therapy (Q3W) and at the follow-up visit. Sensitivity of test must be at least 25 IU/L or equivalent units of 1.human chorionic gonadotropin. CBC plus differential, serum chemistry, and thyroid panel should be drawn within 24 hours prior to each subsequent scheduled cycle. On-study laboratory tests will be performed on site/locally. Laboratory tests may be obtained more frequently if indicated. Any increase in LFTs from baseline must be monitored every 3 days until levels peak and begin to decline. Grade 3 decreases in neutrophil and thrombocytopenia must be repeated within 72 hours. Additional laboratory tests should be performed as per standard of care.

The cTnT or cTnI will be monitored as described in Table 5.1-1 and Table 5.1-2. Grade 1 elevation requires dose interruption of BMS-986183 and nivolumab and repeat assessment within 24 hours. If there is persistent elevation, further dosing should be discontinued. Grade 3 elevation of cTnI or cTnT requires discontinuation of BMS-986183 and nivolumab, and prompt consultation and management with a cardiologist are recommended until it resolves.

If a subject shows pulmonary-related signs (hypoxia, fever) or symptoms (eg, dyspnea, cough, fever) consistent with possible pulmonary AEs, the subject should be immediately evaluated to rule out pulmonary toxicity, according to the suspected pulmonary toxicity management algorithm in the nivolumab IB.

Additional measures, including nonstudy required laboratory tests, should be performed as clinically indicated or to comply with local regulations. Laboratory toxicities (eg, suspected drug induced liver enzyme elevations) will be monitored during the safety follow-up period via on-site/local labs until all study drug toxicities for which no clear alternative cause is identified other than to BMS-986183 resolve, return to baseline, or are deemed irreversible.

Chest X-Ray, ECHO/MUGA, urinalysis, cTnT or cTnI, or ECG may also be performed on-treatment as clinically indicated.

Safety assessments may be shared with investigators at periodic safety teleconferences.

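### Internal inconsistency: after a drug-related Grade 1 troponin elevation, the repeat test that decides discontinuation is timed at 72 hours in Table 4.5.2-1 but within 24 hours in Sections 4.5.4 and 5.3

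*Protocol*

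**What the plan says.** Three places in the protocol govern a Grade 1 troponin elevation on treatment.

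- **Table 4.5.2-1 (Section 4.5.2).** Among the criteria for drug-related adverse events is "Grade 1 Troponin I or T confirmed when repeated in 72 hours". The action given is to discontinue.
- **Section 4.5.4.** Study drug must be held for "Grade 1 Troponin T or I elevation until confirmation". The text then sets the time and the consequence: "within 24 hours. (Subjects with repeat Troponin I or T > 1× ULN will be discontinued".
- **Section 5.3.** "Grade 1 elevation requires dose interruption of BMS-986183 and nivolumab and repeat assessment within 24 hours". It continues: "If there is persistent elevation, further dosing should be discontinued".

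Four other provisions bear on how these are read.

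- Section 4.5.2 says of its own content: "The criteria presented in this section and Table 4.5.2-1 for dose modifications and delays are meant as general guidelines". It also lets the investigator act more conservatively than the table, in consultation with the sponsor or medical monitor.
- Section 3.5 makes stopping mandatory for adverse events that require discontinuation under Section 4.5.2.
- Section 4.5.6, on permanent discontinuation, has no troponin item.
- The SAP contains no troponin rule.

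**The concern.** The trigger (a Grade 1 troponin I or T elevation) and the consequence (stopping drug) are the same in all three places, but the time of the deciding repeat is not. Troponin can rise and fall within days, so the time of the second sample can determine whether the elevation counts as confirmed.

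Two things are at stake. The first is consistent management of subjects in a first-in-human study. Section 1.4.2.1 reports troponin increases with cardiomyocyte damage in rats, and troponin increases without microscopic cardiomyocyte damage in monkeys. The second is the data. Adverse events leading to discontinuation are part of the primary endpoint (Protocol Section 8.3.1, SAP Section 4.1) and are tabulated under SAP Section 7.5.4. Sites that follow different sections could classify the same clinical course differently in those tables.

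**Working it through.** The plan gives no figure to reproduce. The check is a comparison of the texts, followed by the possible courses under each.

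**Side by side**

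| Place | Repeat time | Finding that leads to stopping | Scope |
|---|---|---|---|
| Table 4.5.2-1 | *in* 72 hours | elevation confirmed | drug-related events |
| Section 4.5.4 | within 24 hours | repeat above 1 × ULN | not limited in the troponin item |
| Section 5.3 | within 24 hours | elevation persists | not limited in the troponin sentences |

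The stated times differ by a factor of 72 / 24 = 3, a gap of 72 − 24 = 48 hours.

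**Two readings of the table.** The word *in* can mean *within* 72 hours or *at* 72 hours.

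- *Within.* A repeat done by 24 hours satisfies all three texts. A repeat done in the 48 hours that follow satisfies the table and breaches Sections 4.5.4 and 5.3.
- *At.* The table and the two sections call for samples at different times, and one repeat cannot satisfy both.

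**Possible courses**

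1. Elevated at 24 and at 72 hours: every text leads to discontinuation.
2. Normal at 24 and at 72 hours: no text leads to discontinuation.
3. Elevated at 24 hours, normal by 72 hours: Sections 4.5.4 and 5.3 discontinue. The table read as *at* does not. The table read as *within* gives either answer, depending on when the site takes its sample.

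Course 3 is where the contradiction changes the decision.

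**Is there a reconciling text?** None describes a first repeat at 24 hours followed by a second at 72 hours, and none ranks one section above another. Section 4.5.6 does not settle it. The only other timed troponin repeat is the eligibility rule in Section 3.3.2, under which certain subjects "will be permitted if repeat levels within 24 hours are" at or below the upper limit of normal. That rule concerns entry to the study and does not govern treated subjects.

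**How often could it arise?** Table 5.1-1 schedules troponin at screening and on Cycle 1 Days 1, 8 and 15. Table 5.1-2 then has it as clinically indicated, although Section 5.3.2 also lists it under serum chemistry. The documents give neither the frequency of Grade 1 elevations nor the proportion that resolve between 24 and 72 hours, so no count or range can be derived.

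**Does it change exposure while the result is awaited?** Little. With 21-day cycles the second dose falls on Day 22. An elevation found on Day 8 leaves 22 − 8 = 14 days, and one found on Day 15 leaves 22 − 15 = 7 days. Both exceed 72 hours, which is 3 days. Sections 4.5.4 and 5.3 also hold drug in the meantime. The effect therefore comes through the decision that the repeat produces.

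**The case against.** The strongest defence is that the texts can be lived with. If *in* means *within*, a site that repeats by 24 hours meets all three. The table is labelled general guidance and allows more conservative action, while Sections 4.5.4 and 5.3 are worded as requirements and agree with each other. This narrows the conflict but does not remove it. The other reading of *in* remains open. Section 3.5 turns discontinuations under Section 4.5.2 into mandatory ones, so the table is not merely advisory. Permission to be more conservative also does not define what counts as confirmed.

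Several stronger readings are tempting, and the documents do not support them.

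- *Every Grade 1 troponin elevation is affected.* The decision changes only when the result depends on the timing of the repeat, and the table covers drug-related events only.
- *The rule imposes permanent discontinuation.* The three texts speak of discontinuing without that word, and Section 4.5.6 omits troponin. The inference is reasonable, because the table separates discontinuing from interrupting and from reducing a level, but it remains an inference. Section 4.5.6 also provides for discussion with the medical monitor where continuing may be favourable.
- *The reverse course, normal at 24 hours and elevated at 72, is equally a problem.* Under Section 4.5.4 a normal repeat ends the hold, and no text asks for another test at 72 hours after it.
- *The nonclinical data predict this toxicity in subjects.* The rat findings stand. However, the protocol regards the monkey as the most appropriate species for setting the starting dose, and reports the monkey troponin increases without microscopic cardiomyocyte degeneration or necrosis.
- *A primary analysis is invalidated.* The safety endpoints are summarised descriptively with no formal hypothesis test, and no error rate or estimate can be shown to move.

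**Conclusion.** The inconsistency is real and can be read directly from the text: 72 hours in one place and 24 hours in two others, for the same trigger and the same action. It is a drafting conflict between sections, not a questionable design choice.

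Its demonstrable size is limited. It changes the decision for a subject whose elevation is present at 24 hours and gone by 72. It also puts a site that repeats between those times in breach of two sections while following the third. How many subjects or sites this would involve cannot be determined from the documents.

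The conclusion rests on one assumption: that the three texts address the same event in treated subjects. Their wording supports this for drug-related elevations. It does not depend on which reading of *in* is taken, since a conflict remains under both. It is still worth correcting, because the rule decides who stops drug and who is counted among discontinuations for adverse events.

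**What to change.** Amend Table 4.5.2-1, Section 4.5.4 and Section 5.3 so that they state one repeat-test rule in the same terms. The rule should give:

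- the time of the repeat, and whether it means *at* or *within* that time;
- the result that counts as confirmed;
- which result governs if more than one repeat is taken;
- whether it applies to drug-related elevations only.

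Which time applies is a clinical decision for the sponsor, and no view on it is offered here. The cost is amendment wording and notice to sites. Sample size and the planned analyses are unaffected, and the SAP needs no change because it has no troponin rule.
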